6.6.2 Special Assays or Procedures

Intraoperative plasma samples will be obtained from pre-existing vascular access catheters at end of bolus, 30, 60, 90 minutes, at time of intestinal excision(s), and at the end of the case in ethylenediaminetetraacetic acid microcontainers, exceeding no more than approximately 5 mL total (Figure 2). Additional plasma can be collected if the child remains in the hospital either in the recovery room or on the surgical ward at times 3-4 hours, 4-6 hours, and 6-12 hours from infusion of metronidazole, however these samples are not necessary for a participant to be included in the study analysis. At the time of intestinal excision, the surgeon will cut at least 500 mg of intestine from the specimen, ensuring all layers of bowel are included. If more than one intestinal sample is taken during the surgery, such as in the case of multiple strictures removed, each sample will be obtained and labeled appropriately. The sample(s) will be placed in a sterile, dry container.

All samples will be frozen in liquid nitrogen and stored in a -80°C freezer within 1 hour of acquisition. Samples will be batched and shipped to a central laboratory for concentration measurement of metronidazole and its primary metabolite 2-hydroxymetronidazole using a HPLC/MS/MS plasma assay previously developed and validated per FDA guidance¹³. The plasma and intestine samples will also be assayed for CYP2A6, transporters, and metabolizing enzymes through protein quantification assays at a proteomics laboratory.

Every effort should be made to collect all PK samples, and the timing of PK sampling with standard-of-care blood draws when possible. Collection of PK samples outside the windows provided in the sampling will not be considered protocol deviations.

If a procedure is shorter than the 90 minutes, this PK sample will not be taken. Similarly, if the procedure is less than an hour the 60- and 90-minute samples will not be obtained. Finally, in the unlikely event that

a procedure is less than 30 minutes, only the end of bolus, intestinal excision, and end of case samples will be taken.

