2.1.3 Antibiotic Penetration of the Intestine

Intestinal wall concentrations of antibiotics are essential to treat local bacterial infection and improve outcomes. Failure to reach optimal antibiotic concentrations in the intestinal wall may result in abscess formation, intestinal necrosis, and secondary bacteremia, thus worsening clinical outcomes³. Optimizing intestinal wall concentrations of antibiotics in infants with cIAI is therefore an urgent and unmet public health need. Antibiotic uptake from the blood stream into the intestinal wall and local metabolism determine tissue concentrations, and are complex and understudied processes dependent on perfusion, endothelial integrity, and expression and function of transporters and metabolizing enzymes⁸. These processes are affected by both pathophysiologic alterations of cIAI and by infant growth and maturation⁹. Prior studies attempting to understand this relationship sampled enteric flora or peritoneal fluid, but none directly studied human intestinal tissue¹⁰. These alternate approaches precluded characterization of both intestinal wall absorption and intestinal wall metabolism of metronidazole, the latter occurring primarily via cytochrome P450 (CYP) 2A6.

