6.3 Treatment Procedures

Operative Day (Day 1)

The following assessments will be conducted on the day the patient is administered the study drug and undergoes surgery.

- 1) Date, time, dose, route, and duration of metronidazole administration
- 2) Physical examination and vital signs, including weight, height, heart rate, respiratory rate, oxygen saturation and blood pressure, can be performed prior to intubation on the day of surgery
- 3) Laboratory determinations, if available, no blood draws will be performed just for the purposes of this study (See Section 6.6)
- 4) Concomitant medications of interest
- 5) Collection of PK plasma and intestine samples (including date/time; See Section 6.6.2)
- 6) Results for laboratory tests of interests (See Section 6.6.1)
- 7) Events of special interest (See Section 8.1)
- 8) Adverse events related to study procedures (See Section 8.4)
- 9) Information regarding the surgery performed including: type of surgery, laparoscopic vs. open procedure; times of incision, intestinal excision, closure; intubation, extubation; estimated blood loss, blood transfusions given, amount and type of intravenous fluids given
- 10) Intraoperative complications including: unexpected alteration in operative plan, excessive blood loss, need for transfusion, damage to any structure, conversion from laparoscopic to open procedure, death (See Section 8.2)

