6.6.3 Example PK Sample Schedule

Sample Number	Time after end infusion of metronidazole (min)*	Type of Sample
#1	0 – At end infusion	Plasma
#2	30	Plasma
#3	60	Plasma
#4	90	Plasma
#5	Time of intestinal excision	Plasma
#6	Time of intestinal excision	Intestine
#7	Time of skin closure	Plasma

*Plasma samples will be accepted +/- 10 minutes from ideal blood draw time

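### Bowel may wait up to one hour before freezing and no freezing time is recorded, so any conversion in the specimen could lower the tissue metronidazole:2-hydroxymetronidazole ratio and could not be examined later

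*Combined protocol and SAP*

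**What the plan says.** Section 6.6.2 describes handling. The tissue is taken at surgery: "At the time of intestinal excision, the surgeon will cut at least 500 mg of intestine from the specimen". Then: "The sample(s) will be placed in a sterile, dry container". The next paragraph sets one limit for plasma and bowel alike: "All samples will be frozen in liquid nitrogen and stored in a -80°C freezer within 1 hour of acquisition". It mentions no ice, quenching or immediate snap-freezing, and it does not separate the time to freezing from the time to storage.

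Section 6.3 lists what is recorded. Item 9 asks for "times of incision, intestinal excision, closure; intubation, extubation". Item 5 asks for the date and time of each plasma and intestine PK sample. Neither item lists a freezing time or the time at which the specimen lost its blood supply. In Section 6.6.3, plasma sample #5 and intestine sample #6 share one nominal time: "Time of intestinal excision".

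Section 2.1.3 supplies the scientific premise, "intestinal wall metabolism of metronidazole, the latter occurring primarily via cytochrome P450 (CYP) 2A6". Section 2.1.4 adds that the activity of this enzyme in infant bowel wall, and how it varies between infants, is not known. Section 3 reads the secondary objective from CYP2A6 quantification, the parent:metabolite ratio, and the plasma/intestine ratio of each analyte.

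**The concern.** The study looks for metabolism in the bowel wall, so the specimen may go on doing what is being measured until it is frozen. Once its blood supply is divided, no parent drug arrives and no metabolite is carried away. Unless the metabolite is itself lost, any further conversion moves the tissue parent:metabolite ratio one way, downwards. A lower ratio is also what greater intestinal CYP2A6 activity would produce, so the error resembles the finding.

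If enzyme activity differs with age, conversion during the delay would differ too. It could then imitate the age dependence hypothesised in Section 2.2.

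The delay is likely to vary from case to case. With up to 20 infants and one intestine sample in the example schedule, a delay that was not logged cannot be reconstructed, modelled or shown to be harmless.

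**Working it through.** **Figures in the plan.** The documents give no conversion rate after excision, no expected tissue ratio, no half-life and no typical delay. There is therefore no stated figure to reproduce, and what follows is a sensitivity calculation. The nearest stated figure is the power for a 20% plasma–tissue difference in Section 10.1. It cannot be reproduced because the SD of the paired difference is not given, and this point does not change it.

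**Inputs, all assumed.**
- *m*: tissue metabolite as a fraction of tissue parent when blood supply ends; 0.30 or 0.10.
- *f*: fraction of tissue parent converted before freezing; 0.01 to 0.05.
- Conversion is one-for-one in molar terms, and nothing enters or leaves the specimen.

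**Formula.** Before the delay the ratio is 1/*m*. After it, parent is 1 − *f* and metabolite is *m* + *f*. The observed ratio divided by the true ratio is therefore *m*(1 − *f*)/(*m* + *f*).

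| *m* | *f* | Observed/true ratio | Change in ratio | Change in tissue parent |
|---|---|---|---|---|
| 0.30 | 0.01 | 0.297/0.31 = 0.958 | −4% | −1% |
| 0.30 | 0.05 | 0.285/0.35 = 0.814 | −19% | −5% |
| 0.10 | 0.01 | 0.099/0.11 = 0.900 | −10% | −1% |
| 0.10 | 0.05 | 0.095/0.15 = 0.633 | −37% | −5% |

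The ratio is sensitive because a small share of a large parent pool is added to a small metabolite pool. By the same arithmetic, tissue metabolite rises by *f*/*m*: 3–17% at *m* = 0.30 and 10–50% at *m* = 0.10. The metabolite's plasma/intestine ratio would move accordingly.

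**Pairing with plasma.** A delay to freezing does not alter the pairing of plasma #5 with tissue #6. A mismatch arises only if blood supply ended some time *g* before the excision draw. Plasma parent would then have fallen by 1 − 2^(−*g*/*h*) for half-life *h*, with both values assumed:

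| *g* | *h* = 2 h | *h* = 4 h | *h* = 8 h |
|---|---|---|---|
| 10 min | 5.6% | 2.8% | 1.4% |
| 30 min | 15.9% | 8.3% | 4.2% |

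This is small unless the gap is long or the half-life short.

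**The case against.** The case on the other side has four parts.

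- **The sentence may be read more kindly.** It can mean freezing at once, with -80°C storage complete by one hour. The absence of cooling is inferred from silence. This stands as an ambiguity, but the text does not say so, and an hour's wait would comply with it.
- **Detail may sit elsewhere.** Section 16.4 mentions a manual of procedures, Section 13 a manual of operations if applicable, and Section 10.2 a PK analysis plan. None is available here. However, Section 6.6.2 does not refer tissue handling to any of them.
- **Every size is assumed.** This stands in full. A reader might go further and take metabolite to be 5% of parent, which gives falls of 17.5–52.5%. The upper end would need detached bowel to form, in under an hour, as much metabolite as it already held. Nothing in the documents supports relying on that.
- **The ratio is not the only evidence.** CYP2A6 is also quantified directly, and tissue parent barely moves. This limits the concern to results that depend on tissue metabolite.

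Two stronger readings are tempting and should not be drawn. A reader might infer that excision is the only tissue time recorded, but item 5 of Section 6.3 also captures the intestine sample's date and time. A reader might also infer that tissue is paired with the wrong plasma time. The schedule puts plasma #5 and tissue #6 at the same moment, and the documents describe no gap between loss of blood supply and excision. The planned population PK model could also predict plasma at another time if one were needed.

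**Conclusion.** The point holds as a weakness in sample handling and recording, not as a demonstrated bias. The plan permits a variable delay before bowel is frozen, with no cooling stated, and does not list the time that would allow the delay to be examined. Any conversion in that interval would lower the tissue parent:metabolite ratio and overstate intestinal metabolism.

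The size is unknown. The illustrative falls of 4–19% (metabolite 30% of parent) and 10–37% (metabolite 10%) rest on an assumed 1–5% conversion in a closed specimen with no loss of metabolite. The concern is chiefly the secondary ratio endpoint; primary parent PK is little affected. The change is worth making because it is cheap and the missing information cannot be recovered later.

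**What to change.** 1. In Section 6.6.2, give tissue its own limit, for example: *intestine is snap-frozen in liquid nitrogen as soon as it is cut, target within about 10 minutes of excision; plasma within 1 hour.* The 10-minute target is a suggestion, not a figure derived from the documents.
2. In Section 6.3, add the time of freezing for each intestine sample and, where it can be identified, the time that specimen's blood supply ended. Where several segments are removed, log these for each.
3. In Section 10.2 or the PK analysis plan, pre-specify a sensitivity analysis of the tissue parent:metabolite ratio and of CYP2A6 by delay to freezing. With up to 20 infants this will be descriptive.
4. Keep plasma #5 at excision. If blood supply ended appreciably earlier, compare tissue with model-predicted plasma at that time, using the population PK model already planned.

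The cost is bringing liquid nitrogen, which the protocol already requires, to or near the operating room, and having someone there to log one or two more times. No extra blood, tissue or change to surgery is needed. If conversion proves trivial, the recorded times would help the sponsor show it.

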6.6.3 Example PK Sample Schedule

Sample Number	Time after end infusion of metronidazole (min)*	Type of Sample
#1	0 – At end infusion	Plasma
#2	30	Plasma
#3	60	Plasma
#4	90	Plasma
#5	Time of intestinal excision	Plasma
#6	Time of intestinal excision	Intestine
#7	Time of skin closure	Plasma

*Plasma samples will be accepted +/- 10 minutes from ideal blood draw time

6.7 Concomitant medications

The name, daily dose, and date of administration of each concomitant medication of interest will be recorded for all doses given from day of surgery until the end of the study. Medications of interest include:

- Other systemic antimicrobials
- Oral anticoagulants
- Inducers of CYP 2A6:
 - Rifampicin
 - Barbiturates such as amobarbital, pentobarbital, phenobarbital and secobarbital
- Inhibitors of CYP 2A6 such as:
 - Amiodarone
 - Amlodipine
 - Buprenorphine
 - Clofibrate
 - Clotrimazole
 - Desipramine
 - Disulfiram
 - Entacapone
 - Fenofibrate
 - Gabapentin,
 - Isoniazid
 - Ketoconazole
 - Letrozole
 - Methimazole
 - Methoxsalen

- Metyrapone
- Miconazole
- Modafinil
- Orphenadrine
- Pilocarpine
- Selegiline
- Sulconazole
- Tioconazole
- Tranylcypromine

7 STUDY PRODUCT DESCRIPTION

7.1 Dosage and Study Drug Information

7.1.1 Rationale for Dose Selection

Dosing will not be prescribed by this protocol. Dosing will be per standard of care and at the discretion of the treating physician.

7.1.2 Dose Frequency

Frequency of metronidazole dosing will be at the discretion of the treating physician.

7.1.3 Study Drug

This protocol does not specify the brand of product nor dosing amount or interval. Product will be “off the shelf” metronidazole as determined by the site.

7.1.4 Preparation and Administration of Study Intervention/ Investigational Product

The local pharmacy will prepare the metronidazole per standard of care.

8 ASSESSMENT OF SAFETY

8.1 Events of Special Interest

Events of special interest to be collected include:

1. Gastrointestinal surgeries subsequent to index surgery
2. Intestinal strictures as defined by the primary clinical team
3. Sepsis as defined by the clinical team or positive blood cultures with an organism not typically considered a contaminant
4. Wound infection as defined by clinical team or positive wound cultures with an organism not typically considered a contaminant
5. Urinary tract infection defined as a positive urine culture with an organism not typically considered a contaminant
6. Feeding intolerance as defined by the clinical team or the insertion of any type of decompression or feeding tube
7. Transfusion requirements with any blood product
8. Phlebotomy related issues such as thrombophlebitis, hemorrhage, and thrombus

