Adverse Events ^f	X	X	X
Intraoperative Complications ^g		X	
Postoperative Complications ^g		X	X
Prior and Concomitant therapy	X	X	
Pharmacokinetic data			
PK sample collection			
Plasma sample collection		X	
Intestine sample collection		X	

a: Demographics to be included: gender, date of birth, age, race, comorbidities, gestational age at birth and birth weight

b: May be obtained through review of electronic medical record. All assessment or laboratory collections performed as standard of care only. No assessments or blood draws other than PK data are performed solely for the purposes of this study

c: Vital signs to be included: weight, height, heart rate, respiratory rate, oxygen saturation, and blood pressure

d: Clinical laboratory parameters to be included: WBC, Hg, HCT, Plt, PT, PTT, BUN, serum creatinine, potassium, sodium, AST, ALT, total bilirubin, albumin, prealbumin, ESR, CRP, any blood, tissue, urine cultures as obtained per standard of care

e: Events of Special Interest include: gastrointestinal surgeries, sepsis, wound infection, urinary tract infection, feeding intolerance, transfusion requirements, phlebotomy complications

f: Adverse events related to study procedures (ie phlebotomy)

g: Complications will be assessed through the electronic medical record including excessive blood loss, transfusion requirements, injury to any organ system, infection in any organ system including wound bed, unanticipated return to the operating room, and any unexpected intra- or postoperative occurrence that requires medical or surgical attention

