6.4 Postoperative Period

The postoperative period of 30 days will be followed remotely through review of the electronic medical record. If no clinical contact has been made by the end of the postoperative period, study personnel will phone the parent/guardian to examine for any adverse events or hospitalizations to the participant.

- 1) Information regarding any adverse events related to metronidazole administration and/or study procedures (see section 8.4)
- 2) Information regarding events of special interest (See Section 8.1)
- 3) Information regarding postoperative complications including: any unexpected medical or surgical intervention, readmission for any reason, postoperative blood loss, transfusion requirements, infectious complications of any organ system or the wound, death (See section 8.3)

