10.2 Analysis Plan

Population for Analysis

All enrolled participants with at least 1 evaluable PK sample will be included in the PK analysis and all participants who receive at least 1 dose of study metronidazole will be included in the safety analysis population.

Statistical Methodology

Descriptive statistics, such as number of observations, mean, median, 95% CI, standard deviation, standard error, minimum, and maximum, will be presented by age cohort for continuous variables (such as height, weight, and BMI percentile). Other descriptive statistics, such as counts, proportions, and/or percentages, will be presented by age cohort group to summarize discrete variables (such as race and sex).

Demographics, Baseline Characteristics, and Clinical Course

The number of participants completed and discontinued early from study, and the reasons for discontinuation, will be summarized. Demographic and baseline characteristics will also be summarized. Variables include race, age, sex, ethnicity, and other selected clinical variables will be recorded prior to initiation of study drug. Variables including drug dosing and other selected clinical variables during study drug administration will be recorded.

Safety and Clinical Laboratory Analyses

Laboratory data (serum BUN, serum creatinine, potassium, sodium, AST, ALT, total bilirubin, albumin, prealbumin, ESR, CRP, serum WBC count, Hg, Hct, platelet, PT, PTT) will be tabulated by age cohort. Continuous laboratory measurements will be described using univariable descriptive statistics (mean, median, etc.); observed values and changes from baseline will be summarized. Lab tests reflective of electrolyte abnormalities (e.g., hyponatremia, hypokalemia) will be further summarized in terms of the most extreme values and largest changes from baseline (in the appropriate direction) observed from start of study drug through the end of therapy.

Adverse events and events of special interest will be summarized by age cohort and relationship to drug exposure will be explored. Prior and concomitant medications will be summarized by World Health Organization (WHO) drug class.

PK Analysis

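### Section 8.1 counts a tube inserted on the operative day as planned care as feeding intolerance, and leaves open whether the resected stricture is an event

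*Combined protocol and SAP*

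**What the plan says.** Section 8.1 lists eight events of special interest. Three matter here:

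- Item 6: "Feeding intolerance as defined by the clinical team or the insertion of any type of decompression or feeding tube".
- Item 2: "Intestinal strictures as defined by the primary clinical team".
- Item 1: "Gastrointestinal surgeries subsequent to index surgery".

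Collection starts on the operative day. Table 1 marks these events in the treatment period and the postoperative period, Section 6.3 item 7 lists "Events of special interest (See Section 8.1)" among the Day 1 assessments, and Section 6.4 item 2 continues with "Information regarding events of special interest (See Section 8.1)".

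Section 6.6.2 allows for more than one intestinal specimen, "such as in the case of multiple strictures removed", so a stricture can be the lesion taken out at the index operation.

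Table 1 footnote e gives a shorter list: "Events of Special Interest include: gastrointestinal surgeries, sepsis, wound infection, urinary tract infection, feeding intolerance, transfusion requirements, phlebotomy complications". Strictures are not in it.

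Section 10.2 states the use: "Adverse events and events of special interest will be summarized by age cohort and relationship to drug exposure will be explored".

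**The concern.** An event of special interest should mark something that happened to the infant, not the care that every infant was due to receive. In item 6 the two routes are joined by an 'or', and the second needs only that a tube of any type was inserted. An abstractor who follows the text must record feeding intolerance for a tube placed on Day 1 as a planned part of a bowel operation. An abstractor who applies clinical sense would not. The protocol gives no rule for choosing between them.

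Item 2 has a narrower gap. It carries no limit to new or post-index strictures, so it does not exclude the stricture that was the reason for surgery.

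At stake are the feeding-intolerance figures by age cohort and against drug exposure, and to a lesser degree the stricture figures. With about 10 infants per gestational-age stratum, a few misclassified infants can dominate either summary.

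**Working it through.** The plan states no rate, power or threshold for these events, so there is no figure to reproduce. The check is a reading of the text, followed by an illustration with assumed inputs.

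**Text, side by side**

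| Section | Start of window | Must depart from planned care? |
|---|---|---|
| 8.1 item 6, tube route | none in the item; collected from Day 1 | no |
| 8.1 item 2 | none in the item; collected from Day 1 | left to the clinical team |
| 8.1 item 1 | after the index operation | not applicable |
| 8.2 intraoperative complications | entry to the operating room | yes, management altered to address an issue |
| 8.3 postoperative complications | exit from the operating room, to 30 days | yes, change from standard recovery |

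A planned tube inserted on Day 1 fails the tests in 8.2 and 8.3 but meets item 6. A tube already in place before Day 1 is not an insertion within the window and is not affected.

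**Illustration**

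Inputs: N = 20, 10 per stratum (Section 4.1). Assumed, because the documents give neither: p, the true feeding-intolerance rate, and q, the share of infants with a routine tube inserted in the window, independent of intolerance.

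Recorded rate = p + (1 − p)q. Share of recorded events that are true = p / recorded rate.

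For p = 20%:

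- q = 0: 20%, 4 of 20; all true
- q = 25%: 0.20 + 0.80 × 0.25 = 40%, 8 of 20; 0.20/0.40 = 50% true
- q = 50%: 0.20 + 0.80 × 0.50 = 60%, 12 of 20; 33% true
- q = 75%: 0.20 + 0.80 × 0.75 = 80%, 16 of 20; 25% true
- q = 100%: 100%, 20 of 20; 20% true

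At q = 25%, 50%, 75% and 100%, p = 10% gives recorded rates of 32.5%, 55%, 77.5% and 100%; p = 30% gives 47.5%, 65%, 82.5% and 100%.

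**Effect on a cohort difference**

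If q is the same in both cohorts, recorded difference = (pA − pB)(1 − q). An assumed true difference of 40% against 10%, 30 points, becomes 30 × 0.75 = 22.5 points at q = 25%, 15 at q = 50% and 7.5 at q = 75%.

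If q differs between cohorts, a difference can appear where none exists. With p = 20% in both and q = 25% in one and 75% in the other, the recorded rates are 40% and 80%: a gap of 0.80 × (0.75 − 0.25) = 40 points, due to tube practice alone.

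**Stricture item**

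No arithmetic applies. Item 1 is limited to after the index operation and item 2 is not, while Section 6.6.2 shows that strictures may be the resected lesion. Counting it is therefore permitted. It is not required, because the clinical team supplies the definition.

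**The case against.** The case against has four main parts.

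- **Harm is measured elsewhere.** Section 8.3 covers postoperative complications with a proper window and a severity grade. That is true, and a reader who infers that the trial has no measure of postoperative harm goes too far. But the sentence in Section 10.2 on cohort summaries and drug exposure names only adverse events and events of special interest, so the loosely defined items are the ones that enter those summaries.
- **The stricture reading is only one reading.** This stands. A reader might infer that every infant operated on for a stricture becomes a stricture event on Day 1. The text does not say so: the definition is left to the clinical team, the lesion predates the collection window, and items 3 to 5 and 7 also lack a timing limit. Section 6.2 item 3 records the surgical diagnosis separately, so an index stricture could be recognised at analysis. What remains is a missing qualifier.
- **The size is assumed.** This also stands. The documents do not say how often tubes are inserted as planned care, and they do not support a presumption that most infants receive one.
- **A tube is an objective trigger.** Because follow-up is by record review, requiring a judgement of indication trades sensitivity for subjectivity. The point is fair, but a time limit and a planned or unplanned flag keep the trigger largely objective and do not require proof of intolerance.

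Footnote e introduces its list with a verb that need not be exhaustive, so its omission of strictures is a matter for reconciliation and not evidence of bias.

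**Conclusion.** The point holds for item 6 as a rule that misclassifies when followed: a tube inserted on Day 1 as planned operative care is a feeding-intolerance event. The resulting rate mixes routine care with true events and is hard to interpret by cohort or exposure. A reader might infer that it carries no information about postoperative harm. The documents do not support that, because item 6 also captures clinical-team diagnoses and tubes placed for real intolerance.

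The amount of distortion is unknown. It is nil if no routine tubes are inserted in the window. At an assumed true rate of 20%, the recorded rate doubles once a quarter of infants have one. These figures rest on the assumed p and q and on their independence.

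For item 2 the conclusion is weaker: the resected stricture may be counted, and the wording should say whether it is.

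This should be corrected, but its reach is limited. Section 10.2 attaches no test, threshold or stopping rule to these events, and the PK objectives and the sample size of 20 do not depend on them.

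**What to change.** 1. Redefine item 6, using the limits already in Section 8.3: feeding intolerance as judged by the clinical team, or a new decompression or feeding tube inserted once the infant has left the operating room and not part of the planned recovery pathway.
2. Add to the CRF, for each tube, the time of insertion and whether it was planned or unplanned. Without these fields the distinction can be recovered only by going back to the charts.
3. Limit item 2 to a new or recurrent stricture diagnosed after the index operation.
4. Reconcile Table 1 footnote e with Section 8.1 so that both give the same list.

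The cost is two definition edits, one footnote and two CRF fields. The downside is one chart judgement per tube. These are changes to what is counted, not to how any infant is managed.
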